1.0 Research Design

1.1 Purpose/Specific Aims

To test the extent to which tailored outreach text messages that provide a cue to action and an intervention that enhances access to poverty-reducing resources, in combination with a primary care literacy promotion program, can improve parenting behaviors, child language development, and social-emotional skill acquisition among low-income Latino children.

A. Objectives

Aim 1: To test the relative efficacy of 3 literacy promotion interventions on parenting behaviors, child language and social emotional skill acquisition among low-income Latino children

Aim 2: To examine mechanisms underlying the effects of the interventions

Aim 3: To conduct a mixed methods process evaluation of the literacy promotion interventions

Research question (RQ) 1: How are the literacy promotion interventions implemented?

RQ 2: What are barriers, facilitators, and modifications made to the interventions?

RQ 3: What are parents' experiences with the interventions?

B. Hypotheses / Research Question(s)

Hypotheses (H) 1A: Children in the ROR + texts arm will have enhanced language and social-emotional skill acquisition, and parents will describe enhanced parenting behavior, as compared to those receiving ROR only

H1B: Children in the ROR + texts + Connecting NJ (formerly Central Intake) arm will have enhanced language and social-emotional skill acquisition, and parents will describe enhanced parenting behavior, as compared to those receiving ROR only or ROR + texts

H2A: Effects of the interventions on child language and social-emotional outcomes will be partially mediated by the home literacy environment.

H2B: The effect of ROR + texts + Connecting NJ child outcomes will be partially mediated by reduction in parent stress and aspects of positive parenting (responsive verbal interactions)

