	(2) Health literacy	Short Assessment of Health Literacy (SAHL)	Enrollment	2.5 minutes
	(3) Discrimination	Discrimination Questionnaire	Enrollment	4 minutes

Process measure	(4) Reach Out and Read Receipt	ROR Receipt Questionnaire	Enrollment, 9 m, 18 m	4 minutes
Primary Outcomes	(5) Language skill acquisition	Expressive One-Word Picture Vocabulary Test - Fourth Edition (EOWPVT-4) Spanish-Bilingual - Complete	18 m	5-20 minutes
		MacArthur Bates CDI	Enrollment, 9 m, 18 m	20 minutes
	(6) Social-emotional skill acquisition	Devereux Early Childhood Assessment (DECA)	Enrollment, 9 m, 18 m	5 minutes
	(7) Shared reading (Parent investment) and parent responsiveness	Modified StimQ Read scale	Enrollment, 9 m, 18 m	5 minutes
		StimQ Parental Verbal Responsiveness	9 m, 18 m	6 minutes
		DialogPR Observation of parent-child interactions	9m, 18 m	4 minutes
	(8) Positive and negative parenting behaviors	Parenting Your Infant, Parenting Your Toddler	Enrollment, 9 m, 18 m	4 minutes
		Parent Discipline Questionnaire	Enrollment, 9 m, 18 m	< 1 minute
Secondary outcomes	(9) Reading attitudes and knowledge	Parent Reading Belief Inventory (PRBI)	9 m, 18 m	3 minutes
	(10) Access to community resources	Adapted Survey of Income and Program Participation (SIPP)	Enrollment, 9 m, 18 m	2 minutes
	(11) Parent-clinician relationship	Modified Physician-Parent Communication Survey	Enrollment, 9 m, 18 m	2 minutes
	(12) Parent stress and wellbeing	Adapted LINK survey	Enrollment, 9 m, 18 m	8 minutes
		Parental Stress Scale	Enrollment, 9 m, 18 m	3 minutes
	(13) Child media use	Modified ScreenQ-I/T 2.0 (Infant/Toddler)	Enrollment, 9 m, 18 m	6 minutes

C. Study Duration

Up to 5 years; participants will be involved up to 2 years.

D. Endpoints

Study participation will conclude upon completion of data collection

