1.5 Sample Size Justification

We will recruit 630 Latino parent-child dyads (210 per arm) over a 24-month time period (Months 3-27). This sample size will be sufficient to achieve 80% power to detect a 0.3 standard deviation (SD) difference in language scores between (1) ROR + texts and ROR only and (2) ROR + texts + Connecting NJ and ROR + texts, assuming 20% attrition based on our ongoing work at one of the CHCs. An effect size of 0.3 SD difference would be clinically meaningful since it would be associated with a detectable difference in later cognitive functioning, based on work from a prospective cohort. The proposed sample size will provide 99.9% power to detect a 0.6 SD difference between the community resource arm and ROR only, based on the expected additive effects of the text message and enhanced access to poverty-reducing resources. We will plan for a conservative 24-month recruitment time period to account for seasonal variation in patient volumes and holidays to recruit the target sample (~2-3 participants /site/week).

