6.0 Data Management Plan

6.1 Data Analysis

1. Enrollment: We will recruit 630 parent-child dyads (210 per arm) over a 24-month time period. We expect that 80% of the 630 enrolled parent-child dyads will complete the study, leaving 525 parent-child dyads (175 in each arm).

2. Sample size and power:

630 parent-child dyads (210 per arm) will be sufficient to achieve 80% power to detect a 0.3 standard deviation (SD) difference in the primary endpoints language scores on the EOWPVT-4 and social-emotional skill scores on the DECA at 18 months between (1) ROR + texts and ROR only and (2) ROR + texts + Central Intake and ROR + texts, assuming approximately 20% attrition based on our past work²⁹ and using 0.05 significance level. An effect size of 0.3 SD difference would be clinically meaningful since it would be associated with a detectable difference in later cognitive functioning, based on work from a prospective cohort.³⁰ The proposed sample size will provide 99.9% power to detect a 0.6 SD difference between the community resource arm and ROR only, based on the expected additive effects of the text message and enhanced access to poverty-reducing resources.

3. Analysis:

Distributions of baseline characteristics will be summarized overall as well as by randomization group. We will assess the distribution of outcome data using descriptive statistics to check the assumption of normality for continuous variables. We will estimate mean outcomes for each treatment group as well as mean differences between groups (with confidence intervals). If any continuous outcomes are skewed, we attempt log-transformation or other to stabilize the variance and normalize distributions.

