For aim 1, analysis will follow the intention to treat principle, in which participants are analyzed based on their group assignment, whether or not they receive the strategies for all outcomes. Because of the multiple, potentially highly correlated outcomes, the step-down minP method (a re-sampling approach), will be used to assess the effects of treatment³¹ across outcomes and timepoints within each domain (language development, social-emotional development, and parenting). We will use ANOVAs to evaluate treatment effects on adjusted outcomes. Specifically, for outcomes with more than one post-treatment timepoint and a baseline assessment, we will calculate individual- and baseline-adjusted outcomes from linear models with random individual-specific intercepts (random effect) and treatment and baseline as fixed effects. Then, the adjusted outcome is estimated as the observed outcome minus the best linear unbiased predictor (BLUP) of individual-specific intercept and baseline contribution. For outcomes with one post-treatment timepoint and a baseline assessment, a baseline-adjusted outcome

will be estimated from ANCOVA results as the observed outcome minus the estimated intercept and baseline contribution. The differences in means from ANOVAs focused on these adjusted outcomes will estimate treatment effects. For secondary outcomes, statistical significance will be set at $p < 0.05$ without adjustment for multiple comparisons. For language outcomes, we will adjust for child age and sex in sensitivity analyses.

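### The data table, Section 1.5 and Section 6.1 give different primary endpoints, and no rule says whether a parenting-only or 9-month-only effect makes the trial positive

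*Combined protocol and SAP*

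**What the plan says.** The combined protocol and SAP identifies the primary endpoints in three places.

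- **Section 1.3 B (Data Points table).** The label "Primary Outcomes" covers constructs (5) to (8). These are language (EOWPVT-4 at 18 months; CDI), social-emotional skills (DECA), "7) Shared reading (Parent investment) and parent responsiveness" (StimQ Read, StimQ Parental Verbal Responsiveness, DialogPR, observed interactions) and "8) Positive and negative parenting behaviors" (the Parenting Your Infant/Toddler surveys and the Parent Discipline Questionnaire). All except the EOWPVT-4 are collected at both 9 and 18 months. The secondary label starts at construct (9) and runs to (13).
- **Section 1.5.** The sample size gives "80% power to detect a 0.3 standard deviation (SD) difference in language scores". No instrument or visit is named, and social-emotional skills are not mentioned.
- **Section 6.1, item 2.** The same power is claimed for the "primary endpoints language scores on the EOWPVT-4 and social-emotional skill scores on the DECA at 18 months".

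The Aim 1 analysis in Section 6.1, item 3, applies step-down minP across outcomes and timepoints within three domains: language, social-emotional and parenting. It then says: "For secondary outcomes, statistical significance will be set at" p < 0.05, with no multiplicity adjustment. Hypothesis H1A in Section 1.1 joins the child and parenting gains: "Children in the ROR + texts arm will have enhanced language and social-emotional skill acquisition, and parents will describe enhanced parenting behavior". H1B has the same form.

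**The concern.** A trial should have one list of primary endpoints and one rule for what counts as success. This plan has three statements that differ in measures and visits, and no text ranks them.

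Two things depend on the choice. The first is the headline. Suppose parent-reported shared reading improves at 9 months while the EOWPVT-4 and DECA at 18 months are null. The data table allows that to be reported as a primary result; the power paragraph does not. The case is realistic. Section 1.4 reports that texts improved the home literacy environment in an earlier trial and that effects on child outcomes are unknown. H2A treats the home literacy environment as a mediator of the child outcomes, so a gain on the mediator could be presented as success of the trial.

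The second is the multiplicity rule. If the power paragraph defines what is primary, the CDI and parenting measures could be classed as secondary and fall under the unadjusted rule, although the domain wording also places them under minP.

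**Working it through.** **1. Count the endpoints (post-baseline measure-by-visit combinations).**

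| Source | Language | Social-emotional | Parenting | Total |
|---|---|---|---|---|
| Section 6.1, item 2 | 1 (EOWPVT-4, 18 m) | 1 (DECA, 18 m) | 0 | 2 |
| Section 1.3 B | 3 (EOWPVT-4 at 18 m; CDI at 9 and 18 m) | 2 (DECA at 9 and 18 m) | 12 (6 measures × 2 visits) | 17 |
| Section 1.5 | language scores, unspecified | none | none | – |

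The table may intend DialogPR and the observation as one entry. Parenting is then 5 × 2 = 10 and the total 15.

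**2. Reproduce the stated power.** Inputs from Section 6.1: difference 0.3 SD, alpha 0.05, 175 completers per arm. Sidedness is not stated; two-sided reproduces the plan's figure.

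Power = Φ(δ√(n/2) − z) with δ = 0.3 and n = 175. The first term is 0.3 × √87.5 = 2.806.

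- 0.3 SD: Φ(2.806 − 1.960) = Φ(0.846) = 80.1% (79.9% by noncentral t). The plan says 80%.
- 0.6 SD: Φ(5.612 − 1.960) = 99.99%. The plan says 99.9%.

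Both agree. Each is the power of one contrast on one endpoint with no adjustment.

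**3. What the 80% becomes under possible success rules.** One contrast, 175 per arm, true effect 0.3 SD on each endpoint concerned.

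- *Either of two primaries counts, alpha split by Bonferroni to 0.025:* Φ(2.806 − 2.241) = Φ(0.565) = 71.4% for each endpoint. Restoring 80% needs 2 × (2.241 + 0.842)² / 0.3² = 211.2, so 212 evaluable per arm.
- *Either counts, each at 0.05:* power stays at 80.1% per endpoint, but the chance of at least one false claim is 1 − 0.95² = 9.75% if the two are independent.
- *Both must succeed, each at 0.05:* no split is needed, but joint power is 0.801² = 64.2% if independent, rising towards 80.1% as correlation rises.
- *Constructs (5) to (8) primary, adjusted within domain:* power for an endpoint tested at the strictest step, with Bonferroni as a conservative stand-in for minP, is 66.0% for language (3 tests), 71.4% for social-emotional (2) and 47.6% for parenting (12). With an assumed common correlation of 0.7 these become about 69%, 73% and 56%.

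Section 6.1 also equates 80% of 630 with 525 completers; 0.80 × 630 = 504, or 168 per arm. That is a separate point. At 168 the unadjusted power is 78.5% and the split-alpha power 69.4%.

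**4. Error across domains.** If each of three domains is held at 0.05 and any one counts as success, the chance of at least one false domain claim is 1 − 0.95³ = 14.3% per contrast under independence. With assumed between-domain correlation of 0.3 to 0.7 it is 13.6% to 10.9%. This follows from controlling each domain separately; it does not measure the effect of the inconsistent lists.

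**The case against.** The strongest reply is that the analysis rule already settles most of this. Item 3 of Section 6.1 names parenting as a minP domain and speaks of outcomes and timepoints in the plural. If only the EOWPVT-4 and DECA at 18 months were meant, each child domain would hold one test, there would be no parenting domain, and minP would have nothing to adjust. The rule makes sense only with constructs (5) to (8), which leaves the unadjusted rule for constructs (9) to (13). This stands. A reader might infer that the CDI and parenting measures could escape adjustment altogether; the documents do not support that. What remains is that the power paragraph's label permits a competing reading that no text excludes.

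Next, the power paragraph is the outlier. Aim 1, H1A, H1B and the data table all treat parenting as a full target, so demoting it is not the obvious repair. This also stands, and the fix therefore offers both directions.

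Third, a reader might say the trial was not sized for the parenting measures. That is too strong. Sizing is in SD units, so 175 per arm gives the same 80% for any continuous endpoint at 0.3 SD and unadjusted 0.05. What is missing is a justified effect size for those measures and any allowance for the adjustment.

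Last, Sections 1.10 and 6.4 D plan trial registration, which the timetable places before Year 1. That record may fix the primary outcomes. It is not available here, so nothing is assumed either way. These documents do not fix them.

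The objection does not supply a success rule. Even with minP settled, nothing says whether one domain, all domains or only the child endpoints decide the trial.

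**Conclusion.** The point holds as an inconsistency in current text. The primary set is 2 endpoint-visits in Section 6.1, 15 to 17 in the data table, and unspecified language scores in Section 1.5. The documents therefore leave open whether a parenting-only or 9-month-only effect is a primary success, and they allow the CDI and parenting measures to be read as unadjusted secondaries under one label.

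The stated 80% is arithmetically right for a single unadjusted test. It is about 71% per endpoint if alpha is split across two primaries. This assumes two-sided testing, a true effect of 0.3 SD, 175 completers per arm and Bonferroni.

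The roughly 11% to 14% figure should be quoted only as the error across three separately controlled domains if any one counts as success. A reader might take it as the cost of the mismatch. The documents do not support that, since it would arise under the data table's list alone.

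**What to change.** Use one primary list in Sections 1.3 B, 1.5 and 6.1 (items 2 and 3). Either of two versions would do:

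- **Option A.** Name the EOWPVT-4 and DECA at 18 months as the primary endpoints for the child conclusion. State whether either or both must succeed, and how alpha is handled between them.
- **Option B.** Keep constructs (5) to (8) primary by domain, and reword item 2 of Section 6.1 so that the EOWPVT-4 and DECA at 18 months are described as the endpoints used for sizing.

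Under both options:

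- State that step-down minP covers all of constructs (5) to (8), and that the unadjusted 0.05 rule applies only to constructs (9) to (13).
- State that claims are made per domain, so that a parenting effect does not support a child-outcome claim.
- State that the 80% power is for one unadjusted contrast on one endpoint, and give the figure that applies under the chosen rule.

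The cost is wording; no extra data are needed. The investigators give up some freedom in the headline claim and must report a less favourable power figure. Under Option A, a CDI-only or parenting-only effect becomes supportive, and the H1A and H1B wording in Section 1.1 should be aligned with that.

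### No method is given for missing outcomes, and the EOWPVT-4, measured once with no baseline, has no stated model, so its comparison would rest on observed scores only

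*Combined protocol and SAP*

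**What the plan says.** In section 6.1 (3. Analysis), the Aim 1 "analysis will follow the intention to treat principle", explained as analysis by assigned group whether or not the strategies were received. Treatment effects are differences in means from ANOVAs on adjusted outcomes, tested by step-down minP across outcomes and timepoints within each domain.

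Two adjustment rules are given:

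- **Baseline and more than one later timepoint:** the observed outcome less the predicted individual intercept and the baseline contribution.
- **Baseline and one later timepoint:** the adjusted value is defined "as the observed outcome minus the estimated intercept and baseline contribution".

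The only sensitivity analysis named is adjustment of language outcomes for child age and sex. The protocol says nothing on how a missing outcome is handled.

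The Data Points table (section 1.3 B) lists the EOWPVT-4 as a primary outcome at 18 months only. The CDI and DECA are scheduled at enrolment, 9 and 18 months.

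On numbers, section 6.1 states "We will recruit 630 parent-child dyads (210 per arm) over a 24-month time period", then "We expect that 80% of the 630 enrolled parent-child dyads will complete the study", "leaving 525 parent-child dyads (175 in each arm". The power statement is made "assuming approximately 20% attrition based on our past work".

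**The concern.** An ANOVA needs a score for each dyad it includes. A child without an 18-month EOWPVT-4 contributes nothing, and with no earlier score on that test a repeated-measures model of the EOWPVT-4 alone cannot recover the child. The CDI and DECA are analysed as outcomes in their own right, but the plan does not use them to predict a missing EOWPVT-4.

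If lower-scoring children leave the ROR-only arm more often than the other arms, its completers look better than the group randomised and the intervention effect is understated. The opposite pattern overstates it. Because nothing is pre-specified, the handling of roughly one dyad in six to one in five on a primary endpoint would be chosen after the data are seen.

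**Working it through.** **1. The plan's power figure.** Inputs from section 6.1: difference 0.3 SD, power 80%, "using 0.05 significance level". Sidedness is not stated; two-sided is assumed because it reproduces the figure.

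- n per arm = 2(1.960 + 0.842)² / 0.3² = 174.4, so 175.
- Power at 175 per arm = Φ(0.3/√(2/175) − 1.960) = Φ(0.846) = 80.1%.

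The stated 80% is reproduced with 175 per arm, the number of completers. The power statement therefore already assumes that only completers are analysed.

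**2. The number without a score.**

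- From 525 completers: 630 − 525 = 105 (16.7%).
- From 80% completion: 630 × 0.80 = 504, or 168 per arm; 630 − 504 = 126 (20%). Power at 168 per arm is 78.5%.

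The two statements disagree, since 525/630 = 83.3%. The stated 210 per arm equals 175 × 1.20, whereas 175/0.80 = 219.

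**3. Which rule covers the EOWPVT-4.** Both adjustment rules require a baseline assessment. Section 1.9 describes the test as one for children aged 2 and over, given at the 18-month visit, and children enrol at 6 to 12 months. Neither rule applies, so no model is stated for this endpoint. That dyads would be dropped is an inference from an ANOVA on the raw score.

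**4. When observed-score analysis is biased.** Simulation with a true difference of 0.30 SD and assumed retention (control/intervention), 2 million per arm:

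| Retention | Relation of retention to outcome | Estimate |
|---|---|---|
| 90%/70% | none | 0.30 |
| 80%/80% | same in both arms | 0.30 |
| 80%/80% | opposite in the two arms | -0.01 |
| 70%/90% | same form in both arms | 0.16 |
| 90%/70% | same form in both arms | 0.37 to 0.43 |

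Unequal retention is neither sufficient nor necessary for bias. What matters is outcome-related missingness that differs between arms in form or amount.

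**5. Size under milder assumptions.** Let X be the standardised 9-month score, r its correlation with the EOWPVT-4, and let dropout be logistic in X. Then bias = r × (mean X among retained, intervention − mean X among retained, control). The retained means come from numerical integration.

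- Loss 25% control, 15% intervention; odds ratio 0.67; r = 0.4: 0.4 × (0.0588 − 0.0972) = -0.015 SD.
- Loss 28% control, 12% intervention; odds ratio 0.5; r = 0.6: 0.6 × (0.0789 − 0.1777) = -0.059 SD.

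These are 5% and 20% of the 0.3 SD target. The standard error of the difference is √(2/175) = 0.107 SD, so they are about 0.14 and 0.55 standard errors.

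**6. What imputation recovers (same two scenarios).**

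- All dropouts attended 9 months: residual bias within about 0.005 SD.
- Half left before 9 months: about -0.006 to -0.008 SD in the milder scenario and -0.019 to -0.027 SD in the stronger, depending on how the missing 9-month score is filled.
- All left before 9 months: nearly all of the bias remains (about -0.012 to -0.055 SD across the two).

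The last two cases assume, where baseline data are used, a correlation of 0.3 between baseline and 9-month score.

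**The case against.** The strongest reply is that the plan anticipates the loss. Its power rests on completers, and its intention-to-treat wording concerns assignment versus receipt, with no promise that all 630 dyads will be analysed. Both points stand. A reader might infer a contradiction of intention to treat or an unplanned loss of power; the documents support neither. What they show is an omission.

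A reader might also infer that the written adjusted-outcome rule itself removes dyads from the EOWPVT-4 comparison. It cannot, because it does not apply to an outcome without a baseline.

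Differential retention is not documented either. Arms 2 and 3 receive three texts a week, and arm 3 also a case-manager call, while no contact with arm 1 between visits is described, so a difference is plausible. But tracking contacts and gift cards apply to every arm, and the process measures count parents who ask to stop the texts, so even the direction is uncertain. The loss splits, odds ratios and correlations above come from no document.

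Finally, near-complete recovery by imputation is partly built in, because dropout was made to depend on the very score used to impute. It fails for early leavers. Enrolment data are also thin: section 1.9 gives the infant CDI form from eight months, while enrolment starts at six.

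**Conclusion.** The point holds as an omission with a cheap remedy. The plan has no missing-outcome method and no stated EOWPVT-4 model, and its own figures imply 105 to 126 dyads without the 18-month score. It would go too far to say that the result is biased whenever retention differs by arm: bias requires missingness related to outcome differently between arms.

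Under the milder assumed scenarios the bias is about -0.015 to -0.06 SD, at most about half a standard error. It can be larger, or of opposite sign, if dropout depends more strongly on the outcome itself. Imputation is worth having, but its benefit depends on how many dropouts reach the 9-month visit, which the documents do not give.

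**What to change.** 1. State the model for the EOWPVT-4 explicitly.
2. Analyse all randomised dyads with multiple imputation within arm, using enrolment and 9-month CDI and DECA, 18-month CDI where present, age, sex and clinic.
3. State how the imputation combines with step-down minP, or report it as a pre-specified analysis alongside the minP test on observed scores.
4. For repeated outcomes, use a likelihood model with treatment-by-visit terms, or the same imputation.
5. Add a delta-shift sensitivity analysis by arm, since missing at random cannot be verified.
6. Report missingness by arm and visit, so that a reader can see how many dropouts had 9-month data.
7. Reconcile the 80% completion figure with 525 completers.

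Cost: SAP text and additional analysis work, including some real effort to join imputation to a resampling test. No new data or visits are needed. The downside is reliance on missing at random, which item 5 probes.

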1.3 Research Design and Methods

The proposed research integrates a randomized clinical trial with a mixed methods process evaluation. The goal of this proposal is to test the relative efficacy of 3 approaches to literacy promotion in promoting language and social-emotional skill acquisition among low-income Latino children and enhanced parenting behaviors in their caregivers. Given that early childhood experiences are critical for school readiness and the importance of parent behaviors including shared reading for development and behavior beginning in infancy, this proposal includes both children and their parents as subjects. Beginning in year 1, for Aim 1, we will recruit 630 parent-child dyads to participate in a longitudinal 3 arm randomized clinical trial. All participants will receive Reach Out and Read, which is a standard of care, in which a pediatrician distributes a book to the family and provides guidance on shared reading.

In Aim 1, 630 parent child-dyads will be recruited. Participants will be randomly assigned to one of three study arms: (1) Reach Out and Read; (2) Reach Out and Read + outreach text messages; (3) Reach Out and Read + outreach text messages + Connecting NJ (which will facilitate access to poverty-reducing resources based on the families' needs). We anticipate 210 parent-child dyads in each of the 3 study arms. Children will be ages 6 to 12 months at the time of enrollment. All participants will be asked to participate in an enrollment visit and 2 follow-up visits at 9 months and 18 months; the study will end at 18 months. Each visit will last approximately 90 minutes each in order to complete outcome measures.

The process evaluation will be occurring as the study is being conducted to examine how the three study arms are implemented over time.

A. Research Procedures

All research activities will be conducted by Rutgers study staff. We will be recruiting participants from community health centers: Eric B. Chandler Health Center (Chandler), Jewish Renaissance Medical Center (JRMC), and St. Peter's Family Health Center (St. Peter's) will be the primary sites; Robert Wood Johnson Medical Group at Somerset (Somerset) and Bristol Myers Squibb (BMS) will be secondary/back-up sites due to their smaller patient panels.

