For the mediation analyses in Aim 2, we will examine the extent to which the home literacy environment mediates the effect of the interventions on language skill and social-emotional skill acquisition using the product of coefficients method with each outcome at each post-intervention timepoint individually.³² We will calculate bootstrap bias-corrected confidence intervals ($n=5,000$) to estimate the proportion of treatment effect explained via the home literacy environment. While we expect the effect of the ROR + text messages (arm 2) intervention will mainly operate through the home literacy environment (parent investment) based on our conceptual framework, we expect that the ROR + text + Connecting NJ (arm 3) intervention will also have effects on parenting stress and other responsive parenting interactions (parental verbal responsiveness) through increased access to poverty-reducing community resources accounting for the greater hypothesized impact. We will test this more complex conceptual framework based on an adaptation of the Gershoff model using Structural Equation modeling without latent factors.

For aim 3, the mixed methods approach will allow us to systematically compare data on intervention implementation with the perspectives of parents and clinicians in an ongoing manner. Integration of quantitative and qualitative data will occur at the design, methods, and reporting levels. We will use a convergent design in which we collect quantitative data on key intervention components in the same time frame as we conduct observation (if possible) of study visits.

Parent-child observations will be analyzed by the study team, led by [name]. The observations will be coded according to parent-child interactive behaviors (did expected behaviors occur or not).

Practice and clinician surveys and clinician interviews will be analyzed using qualitative methods to identify changes and adaptations to ROR implementation protocols over time. The evaluation aims to determine what was implemented, how it was implemented, and what changes occurred to implementation over time. We also seek to understand how clinic context affected implementation. These qualitative findings will help inform our quantitative patient-reported outcomes.

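### The Aim 1 outcome models have no clinic term although dyads come from up to five clinics; this gives up a little precision, most clearly for EOWPVT-4, and does not affect validity.

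*Combined protocol and SAP*

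**What the plan says.** All places are in the combined protocol and SAP.

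- **Models (section 6.1, item 3, Aim 1).** Outcomes with a baseline and more than one follow-up get a linear model with a random individual intercept and "treatment and baseline as fixed effects". The predicted intercept and the baseline contribution are subtracted, and an ANOVA is run on what remains. Outcomes with a baseline and one follow-up get an ANCOVA-based adjustment. Child age and sex enter only sensitivity analyses of language outcomes. Clinic appears nowhere.
- **Clinics (sections 1.3 A and 1.9 A).** Three primary health centers are named, plus two described as "secondary/back-up sites due to their smaller patient panels".
- **Allocation (sections 1.3 A and 1.6 A).** Participants are randomly assigned to three arms. Stratification by clinic is neither stated nor ruled out.
- **Clinic differences (sections 1.3 A and 6.1).** The expert interviews are meant to help compare ROR as intended with adaptations made by clinicians or clinics. The Aim 3 analysis adds: "We also seek to understand how clinic context affected implementation".
- **Timing (section 1.3 B table; section 1.9 A).** EOWPVT-4 is given at 18 months only. DECA and CDI are collected at enrollment, 9 and 18 months.
- **Power (section 6.1, item 2).** The sample is called "sufficient to achieve 80% power to detect a 0.3 standard deviation (SD) difference", "using 0.05 significance level". Item 1 expects 175 completers per arm.

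**The concern.** ROR is delivered by the clinic in all three arms, and section 1.2 credits it with effects on shared reading and language, which are trial outcomes. If delivery or patient mix varies between clinics, clinic means can differ. Any part of that variation not removed by other terms stays in the error variance of the treatment comparison.

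Clinic is known for every dyad before randomisation and needs no new data. With individual randomisation, a clinic factor removes between-clinic variation and corrects chance imbalance of arms across clinics. The cost of leaving it out is a somewhat wider confidence interval.

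The point bears most on EOWPVT-4, one of the two endpoints named in the power statement. It has no baseline, so neither adjustment in section 6.1 applies to it, and its main analysis as written has no covariate at all.

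**Working it through.** **Inputs from section 6.1:** difference 0.3 SD, level 0.05 (taken as two-sided, which the plan does not state), 175 completers per arm. **Assumed:** the clinic share of outcome variance, ρ, shown over 1% to 10%, because the documents give none.

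**1. The plan's own figure.** The per-arm size for 80% power is 2 × (1.960 + 0.842)² / 0.3² = 174.5, rounded up to 175. At 175 per arm the noncentrality is 0.3 / √(2/175) = 2.806 on 348 degrees of freedom, which gives power 79.9% (80.1% by the normal approximation). For 0.6 SD power is 99.99%, consistent with "99.9% power to detect a 0.6 SD difference". The stated power therefore reproduces with no clinic term.

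**2. Effect of a clinic term on an outcome with no baseline.** Scale the total SD to 1. With clinic in the model the residual SD is √(1 − ρ), so the noncentrality becomes 2.806 / √(1 − ρ). The equivalent gain in sample size is 1/(1 − ρ) − 1.

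| Assumed ρ | Noncentrality | Power at 175 per arm | Equivalent gain in sample size |
|---|---|---|---|
| 0 (or clinic omitted) | 2.806 | 79.9% | – |
| 1% | 2.820 | 80.3% | 1.0% |
| 3% | 2.849 | 81.1% | 3.1% |
| 5% | 2.879 | 81.9% | 5.3% |
| 10% | 2.958 | 83.9% | 11.1% |

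Spending four degrees of freedom (344 instead of 348) changes none of these powers by more than about 0.01 points.

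**3. Simulation check.** Two arms of 175, five clinics with assumed shares of 30%, 27%, 27%, 8% and 8%, and 4,000 runs per setting (Monte Carlo standard error about 0.3 points at a 5% rejection rate).

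- Simple randomisation: power without and with clinic was 79.8% and 81.5% at ρ = 5%, and 80.5% and 83.4% at ρ = 10%. Type I error without clinic was 4.8% to 5.6% for ρ from 0 to 10%, with no trend away from 5%.
- Allocation stratified by clinic: type I error without clinic was 4.0% at ρ = 5% and 3.8% at ρ = 10%, so the test is mildly conservative. With clinic it was 4.6% and 5.0%.

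**4. Outcomes with a baseline and two follow-ups.** A lasting clinic effect is constant within a dyad. It is therefore partly carried by the baseline and by the individual intercept, both of which section 6.1 subtracts. A simulation of that procedure used 504 dyads, five unequal clinics, an assumed within-child correlation of 0.4 to 0.6, and equal clinic effects at baseline and follow-up. A raw share of 5% fell to about 1.4–1.8% of the adjusted outcome, and a raw share of 10% to 1.8–3.1%; about 0.8% is expected by chance alone. The table above overstates the gain for these outcomes. If clinic effects arise only after baseline, less is removed.

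**The case against.** The best defence is that the plan is valid as it stands and the gain may be negligible. No passage says that clinics differ in mean child outcome. The process evaluation asks how ROR is delivered and adapted, which is a different question. At a share of 1% to 3% the gain is 0.4 to 1.2 points of power, and the back-up sites may enrol few dyads or none. All of this stands. It limits the size of the point, but it does not give a reason to leave out a factor that is already known and costs almost nothing.

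Three stronger readings are tempting, and the documents do not support them.

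- **That nothing in the plan removes clinic variation.** For DECA, CDI and the other outcomes measured at enrollment, 9 and 18 months, baseline and the subtracted individual intercept already remove part of it.
- **That omitting clinic is why power falls below 80%.** At the plan's 175 per arm, power is about 80% without clinic. A lower figure appears only if 80% retention is applied literally: 630 × 0.8 = 504, or 168 per arm, with power 78.3%. That is a separate matter of attrition arithmetic, and although a 5% share would bring 168 per arm to 80.3%, a clinic term is not its remedy.
- **That the standard errors are wrong because allocation was stratified.** Stratification is not described, so the conservative test in the simulation is conditional on a fact the documents do not give.

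**Conclusion.** The point holds as a minor, low-cost improvement. No Aim 1 model contains clinic. The omission causes no bias, and under simple randomisation it leaves type I error near 5%. What is lost is precision: for an outcome without a baseline, about 0.4 points of power at a 1% clinic share, 2 at 5% and 4 at 10%, for 0.3 SD at 175 per arm and two-sided 0.05. The loss is clearest for EOWPVT-4 and should be smaller for outcomes already adjusted for baseline and intercept.

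The size rests wholly on the assumed clinic share, and the true value could lie near zero. A reader might infer from the Aim 3 wording that the plan expects clinics to differ in outcome. It says only that clinic context and adaptations will be studied, so between-clinic differences in outcome are plausible but not documented.

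**What to change.** - Prespecify clinic as a fixed factor in the Aim 1 outcome models before any unblinded analysis, starting with EOWPVT-4, whose model would contain treatment and clinic. In the two-step analyses, put clinic in the adjustment model and subtract its estimated contribution together with that of baseline.
- Give a rule for pooling the two back-up sites if they enrol few dyads.
- State whether allocation is stratified by clinic. If it is, resample within clinic for the step-down minP procedure.

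The cost is one model term, a few sentences of SAP text and at most four degrees of freedom (344 left instead of 348 in a two-arm comparison of 175 each). No new data and no change in sample size are needed.
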